### **7.1.2 Multicenter Studies**

This study will have up to 8 different clinical sites enrolling and treating subjects. Depending on enrollment, some sites may run multiple cohorts. Each cohort is

expected to have a maximum of 18 subjects. For all efficacy analyses where investigative site is an explanatory effect and in by-site subgroup analyses, pooling of sites will be performed because one site had only one cohort and a small sample size. The subjects at [name]'s site (007) will be pooled with the subjects for [name]'s site (003) based on both sites being located in the same state and these being the two smallest-enrolling sites in the state.

### **7.1.3 Assessment Time Windows**

Data will be summarized based on the scheduled visits; no visit windowing will be conducted. Visits 4 (Day 1) and 5 (Day 15) must be performed as scheduled based on the protocol, allowing for consistent and reliable efficacy measurements. However, for visit-based safety outcomes (laboratory tests, electrocardiograms, vital signs, neurological exams, ADHD-RS-IV HV, and C-SSRS), baseline is defined as the last recorded measurement prior to first administration of study drug (this can be a scheduled or unscheduled visit).

## **7.2 Efficacy Measurements**

### **7.2.1 Swanson, Kotin, Agler, M-Flynn, and Pelham (SKAMP) Rating Scale**

The SKAMP rating scale is a 13-item independent observer rating of subject impairment (7-point scale) of analog classroom-observed behaviors during the laboratory classroom assessments. Items 1-4 represent an indication of subject attention, items 5-8 are an indication of deportment, items 9-11 assess quality of work, and items 12-13 assess subject compliance with teacher and classroom rules. The specific items associated with these subscales are detailed in Appendix 14.3. In this study, the change from baseline at Day 15 in mean total score of all SKAMP items (or SKAMP-CS) is defined as the primary efficacy parameter. The mean SKAMP-CS on Day 15, the SKAMP-CS at each of the post-dose assessment times on Day 15, the change from baseline at Day 15 in SKAMP-CS at each of the post-dose assessment times, the change from baseline at Day 15 in mean SKAMP-Attention subscale scores (items 1-4), the SKAMP-Attention subscale scores at each of the post-dose assessment times on Day 15, the change from baseline at Day 15 in SKAMP-Attention subscale scores at each of the post-dose assessment times, the change from baseline at Day 15 in mean SKAMP-Deportment subscale scores (items 5-8), the SKAMP-Deportment subscale scores at each of the post-dose assessment times on Day 15, and the change from baseline at Day 15 in SKAMP-Deportment subscale scores at each of the post-dose assessment times are secondary outcome measures. Higher SKAMP-CS scores signify greater behavioral impairment. Therefore, decreases in SKAMP-CS scores over time will indicate improvement in behavior while increases in SKAMP-CS scores over time will indicate worsening of behavior.

The SKAMP rating scale will be collected during each of 7 class sessions at Visits 4 (Day 1) and 5 (Day 15), occurring at 8:00 am, 10:00 am, 12:00 pm, 2:00 pm, 4:00 pm, 6:00 pm, and 8:00 pm of the laboratory classroom days. Three practice classroom sessions for the laboratory classroom day will be conducted at Visit 2.

Missing or invalid data for individual items will be handled by rules specific to the validated SKAMP scale as described in Section 7.1.1.1.

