
Study Design: This is a randomized, double-blind, placebo-controlled, parallel-group, efficacy and safety study in children with ADHD in a laboratory classroom setting. The study will be comprised of 3 periods: Screening (up to 35 days) including a 3 - 5 day ADHD medication washout prior to Day -1, if necessary; Double-blind randomized treatment with either dasotraline (2 mg/day) or placebo for 14 days; and a final safety evaluation 7 days after last dose. Prior to the start of treatment (Day 1) and following the conclusion of the double-blind period (Day 15), subjects will undergo a full-day laboratory classroom evaluation in cohorts of up to 18 subjects. Each laboratory classroom day will include seven 30-minute simulated classroom sessions where trained observers will assess subjects using the Swanson, Kotkin, Agler, M-Flynn, and Pelham (SKAMP) Scale. In addition during each classroom session, a 10-minute math test (Permanent Product Measure of Performance [PERMP]) will be administered to evaluate sustained attention and effort. Seven (± 2) days after the last dose of study drug, subjects will return to the clinic and complete safety assessments.
 
The primary efficacy endpoint will be the change from baseline to Day 15 in ADHD symptoms as measured by the mean SKAMP-Combined score obtained from an average of the 7 SKAMP assessments collected across the 12-hour classroom day. The SKAMP is a validated 13-item rating scale that assesses manifestations of ADHD in a classroom setting through a combined score and 2 subscale scores; deportment items (interacting with other children, interacting with adults, remaining quiet, staying seated, complying with the teacher’s directions, and following the classroom rules) and attention items (getting started, sticking with tasks, attending to an activity, making activity transitions, completing assigned tasks, performing work accurately, and being neat and careful while writing or drawing). The PERMP is a 5-page math test consisting of 80 problems per page (total of 400 problems); both attempted problems and correct problems will be assessed. Subjects are to complete as many problems as possible in 10 minutes. The appropriate math level for each subject is determined based on results of the math pretest administered at screening.

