11.3. Efficacy Assessments

Swanson, Kotkin, Agler, M-Flynn, and Pelham (SKAMP) Scale

The SKAMP is a validated 13-item rating scale that assesses manifestations of ADHD in a classroom setting through a combined score and 2 subscale scores; deportment items (interacting with other children, interacting with adults, remaining quiet, staying seated, complying with the teacher's directions, and following the classroom rules) and attention items (getting started, sticking with tasks, attending to an activity, making activity transitions, completing assigned tasks, performing work accurately, and being neat and careful while writing or drawing).

Permanent Product Measure of Performance (PERMP)

The PERMP is a 5-page math test consisting of 80 problems per page (total of 400 problems). Both attempted problems and correct problems will be assessed. Subjects are to complete as many problems as possible in 10 minutes.

The appropriate math level for each subject is determined based on results of a math pretest administered at screening.

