##### **7.1.1.1 Missing Individual Items in the SKAMP Scale**

Missing or invalid data for individual items will be handled by rules specific to the validated SKAMP scale as follows:

- If 3 or more individual items in the SKAMP have missing or invalid data, the SKAMP-CS will be set to missing.
- If 1 or 2 individual items in the SKAMP are missing or invalid, the values for the missing individual items will be imputed using the mean of the non-missing individual items for the particular subject at that visit and time point, rounded to the nearest integer.
- If any item within a SKAMP subscale is missing or invalid, the entire subscale score will be set to missing.

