
Secondary weight-adjusted dose-level efficacy analyses will also be conducted on the SKAMP. See section 10 for details.

For secondary efficacy outcomes of mean SKAMP-Attention subscale scores, mean SKAMP-Deportment subscale scores, mean PERMP-A, mean PERMP-C, and mean PERMP total score, missing time points will be handled as follows:

If 3 or more time points have missing or invalid scores, the mean score will be set to

missing. If one or two time points have a missing or invalid score, the mean score will be calculated as the average of the scores at the remaining time points. Missing individual items will not be imputed.

Descriptive statistics for the SKAMP-CS, SKAMP-Attention subscale scores, SKAMP-Depression subscale scores, PERMP-A, PERMP-C, and PERMP total scores will be calculated for the change from baseline (Visit 4) at Day 15 (Visit 5), average across all time points and for each time point individually for the laboratory classroom day on Day 15, and will be presented for each treatment as well for the differences between the treatments (dasotraline 2 mg/day vs. placebo) based on the ITT population.

In addition, the secondary SKAMP and PERMP efficacy variables will be analyzed based on a similar ANCOVA model to the one described above for the ITT population. These models will mirror the model used in the primary analysis, with the relevant SKAMP/PERMP score at baseline as a fixed effect in place of the mean SKAMP-CS at baseline.

The observed means, LS means and associated standard error bars will be plotted over time for SKAMP-CS and the PERMP scores for the laboratory classroom day at Baseline (Visit 4) and Day 15 (Visit 5) by treatment group. Change from baseline SKAMP-CS, change from baseline SKAMP subscale scores, and change from baseline PERMP scores will be plotted over time at Day 15 (Visit 5) by treatment group, as well as by subgroup (sex, race, age).

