### 14.3 SKAMP Rating Scale and Subscales

Subscale	Item
Attention	1. Getting started on assignments for classroom periods
	2. Sticking with tasks or activities for the allotted time
	3. Attending to an activity or a discussion of the class
	4. Stopping and making transition to the next period
Department	5. Interacting with other children (e.g., other students)
	6. Interacting with adults (e.g., teacher or aide)
	7. Remaining quiet according to classroom rules
	8. Staying seated according to classroom rules
Quality of Work	9. Completing assigned work
	10. Performing work accurately
	11. Being careful and neat while writing or drawing
Compliance	12. Complying with teacher's usual requests or directions
	13. Following the rules established for the classroom

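### The SAP scores SKAMP-Attention and SKAMP-Deportment from 4 items each, the protocol lists 7 and 6, and SAP 12.2 declares no change

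*SAP*

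**What the plan says.** The protocol describes the SKAMP as a 13-item scale with a combined score and two subscales, and it names the items of each subscale in both the Synopsis and Section 11.3. The Synopsis gives "attention items (getting started, sticking with tasks, attending to an activity, making activity transitions, completing assigned tasks, performing work accurately", followed by neatness in writing or drawing. In Section 11.3 the Deportment list ends, and the Attention list begins, with "and following the classroom rules) and attention items (getting started, sticking with tasks". Teacher compliance and rule-following belong to Deportment. Task completion, accuracy and neatness belong to Attention.

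SAP 7.2.1 uses four groups: "Items 1-4 represent an indication of subject attention, items 5-8 are an indication of deportment, items 9-11 assess quality of work", and items 12-13 assess compliance. The same section ties the Attention endpoints to items 1-4 and the Deportment endpoints to items 5-8. Appendix 14.3 agrees: it puts "10. Performing work accurately" under Quality of Work and "13. Following the rules established for the classroom" under Compliance. Neither of those groups is a listed efficacy endpoint.

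Two further rules depend on the definition. SAP 7.1.1.1 states: "If any item within a SKAMP subscale is missing or invalid, the entire subscale score will be set to missing". SAP 7.5.2 fits each secondary model "with the relevant SKAMP/PERMP score at baseline as a fixed effect". SAP 12.2 says that no changes to the protocol's analysis are planned.

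**The concern.** Two variables share each name. A reader working from the protocol would take the Attention results to cover finishing work, accuracy and neatness, and the Deportment results to cover compliance and rule-following. Under the SAP they cover none of these. Protocol 5.2 names the SKAMP sub scores, with the PERMP, as measures of the secondary efficacy objective, so these are planned endpoints.

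Point differences on the subscales cannot be read until the scale is settled. The definition also carries into the baseline covariate and the missing-item rule. If both definitions stand when the blind is broken, the scoring could be chosen after the results are seen.

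**Working it through.** **Step 1. Items side by side** (Protocol Synopsis and 11.3; SAP 7.2.1 and Appendix 14.3).

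| SAP item | Content | Protocol subscale | SAP group |
|---|---|---|---|
| 1-4 | starting, persisting, attending, transitions | Attention | Attention |
| 5-8 | peers, adults, quiet, seated | Deportment | Deportment |
| 9-11 | completion, accuracy, neatness | Attention | Quality of Work |
| 12-13 | compliance, rules | Deportment | Compliance |

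Both documents give 13 items, and both lists reproduce that total: protocol 7 + 6 = 13; SAP 4 + 4 + 3 + 2 = 13. The protocol's lists therefore cover the whole instrument and are not examples. The SAP's two endpoint subscales use 4 + 4 = 8 items, leaving 5 in neither. SAP Attention keeps 4/7 = 57% of the protocol's items, and SAP Deportment keeps 4/6 = 67%.

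**Step 2. Score range** (0 to 6 per item, SAP 7.1.1). Attention: 7 × 6 = 42 under the protocol, 4 × 6 = 24 under the SAP. Deportment: 6 × 6 = 36 against 24.

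**Step 3. Endpoints affected** (Protocol 6.2). Each subscale has three bullets: change in the day mean (1 comparison), Day 15 score by time (7) and change by time (7).

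- Subscales: 2 × (1 + 7 + 7) = 30 comparisons in 6 bullets.
- SKAMP-Combined: 1 + 7 + 7 = 15.
- PERMP-Attempted and Correct: 14 + 14 + 2 = 30.
- Total 75; 30/75 = 40%.

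If the Day 15 and change models use the same baseline covariate, they give the same treatment difference. The distinct subscale comparisons are then 2 × (1 + 7) = 16.

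**Step 4. Missing-item rule, illustrative.** The documents give no item-missing rate. Assume independent missingness at rate p per item. One time point's subscale score is then set to missing with probability 1 − (1 − p)^k, for k items.

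| p | k = 4 | k = 6 | k = 7 |
|---|---|---|---|
| 0.5% | 1.99% | 2.96% | 3.45% |
| 1% | 3.94% | 5.85% | 6.79% |
| 2% | 7.76% | 11.42% | 13.19% |

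**Step 5. Similarity of the two scores, illustrative.** The documents give no inter-item correlation. Assume equal item variances and a common correlation r. A sum of 4 items then correlates with the n-item sum containing them as √[4(1 + (n − 1)r) / (n(1 + 3r))].

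| r | n = 7 | n = 6 |
|---|---|---|
| 0.3 | 0.918 | 0.937 |
| 0.5 | 0.956 | 0.966 |
| 0.7 | 0.979 | 0.984 |

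**Step 6. What is untouched.** SKAMP-Combined sums all 13 items in both documents. The sample size rests on that endpoint and reproduces: 44 per group at effect size 0.7 gives power 0.901 (43 per group gives 0.894), and 88/(1 − 0.12) = 100.

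**The case against.** The SAP is explicit and consistent within itself, so a programmer following it would derive the variable that it intends. The protocol text describes the instrument without giving a scoring formula, and Protocol 15 leaves details of the statistical methods to the SAP. The affected endpoints are secondary, with no multiplicity adjustment. On the assumptions in Step 5 the two versions are close to interchangeable.

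The missing-data figures also apply only to single time points. SAP 7.5.2 still forms a day mean when one or two of the seven time points are missing. Extending the same assumptions to independence across time points, the day mean would be missing in 0.03%, 0.08% and 0.13% of cases (4, 6 and 7 items) at p = 0.5%, and in 1.3%, 3.7% and 5.3% at p = 2%. The SAP version loses fewer scores, not more. The 40% share depends on the inventory as well. Adding the mean PERMP total listed in SAP 7.4.2 gives 30/76 = 39%. Adding PERMP-Total by time point, as in SAP 7.2.2, gives 30/90 = 33%.

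The points on limited reach and modest numerical effect stand. They do not remove the contradiction. Protocol 15 defers statistical methods, whereas subscale composition is stated twice in the protocol and is not deferred. Dropping 3 of 7 and 2 of 6 named items redefines the outcome, and a high correlation does not make the two scores the same variable. One practical point also stands: revising the protocol text needs Sponsor and IRB approval (Protocol 17.5).

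**Conclusion.** The concern holds. Followed as written, the SAP yields Attention and Deportment scores that differ from those the protocol describes under the same names, and the statement in SAP 12.2 is inaccurate for them. The reach is six of the 13 secondary efficacy bullets in Protocol 6.2, or 30 of the 75 comparisons listed there.

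This conclusion rests on counting items and needs no assumption. The missingness and correlation ranges do rest on assumed inputs and only illustrate the possible size. The actual effect on the results cannot be determined from the documents. The point should be fixed, but it does not threaten the primary analysis.

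**What to change.** Settle one definition before unblinding, by either route:

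- **(a) Score the protocol's item sets.** Attention becomes items 1-4 and 9-11; Deportment becomes items 5-8 and 12-13. Amend SAP 7.2.1 and Appendix 14.3, and apply the subscale missing-item rule to those sets. The cost is SAP wording and a small change to the derivation program.
- **(b) Keep the 4-item versions.** Declare and justify the change in SAP 12.2, naming the items left out of each subscale. The cost is SAP wording. Aligning the protocol description as well would remove the conflict at its source but needs Sponsor and IRB approval. SAP 7.1.2 already describes site enrolment in the past tense, so if an amendment is impractical the SAP 12.2 declaration is the essential part.

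No new endpoints or data are needed under either route.

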## **7.2.2 Permanent Product Measurement of Performance (PERMP)**

The PERMP is a 5 page math test consisting of 80 problems per page (total of 400 problems). Both attempted problems and correct problems will be assessed. Subjects are to complete as many problems as possible in 10 minutes. The appropriate math level for each subject is determined based on results of a math pre-test administered at screening (Visit 2). Performance is measured by the number of math problems attempted (PERMP-A) and the number of math problems correctly completed (PERMP-C). Like the SKAMP, the PERMP will be administered as a practice at Visit 2 and as the final tests at Visits 4 (Day 1) and 5 (Day 15), during each of 7 class sessions occurring at 8:00 am, 10:00 am, 12:00 pm, 2:00 pm, 4:00 pm, 6:00 pm, and 8:00 pm of the laboratory classroom days. In this study, the change from baseline at Day 15 in PERMP-A, PERMP-C, and PERMP-Total (sum of PERMP-A and PERMP-C) scores at each of the post-dose assessment times, the PERMP-A, PERMP-C, and PERMP-Total scores at each of the post-dose assessment times on Day 15, and the change from baseline at Day 15 in mean PERMP-A, PERMP-C, and PERMP Total scores are defined as secondary efficacy measures. Higher PERMP scores signify higher performance and less severe ADHD symptoms. Therefore, increases in PERMP scores over time will indicate improvement of symptoms, while decreases in PERMP scores over time will indicate worsening of symptoms.

No imputation for missing PERMP values will be performed.

## **7.3 Eligibility Criteria and ADHD Symptom Control Assessments**

### **7.3.1 Schedule for Affective Disorders and Schizophrenia for School-Age Children Present and Lifetime version (K-SADS-PL)**

The K-SADS-PL is used at screening to confirm the diagnosis of ADHD.

The K-SADS-PL is a semi-structured diagnostic interview designed to assess current and past episodes of psychopathology in children and adolescents according to Diagnostic and Statistical Manual for Mental Disorders Fourth Edition; Text Revision (DSM-IV-TR) criteria. The K-SADS-PL covers a broad spectrum of most child psychiatric diagnoses, with the exception of pervasive development disorders and personality disorders. The K-SADS-PL includes questions about school performance

and other issues relevant to children and adolescents. There is a base instrument (82 items) and 5 required diagnostic supplements which are completed depending on the results of the base screening: (1) Affective Disorders; (2) Psychotic Disorders; (3) Anxiety Disorders; (4) Behavioral Disorders; (5) Substance Abuse and Other Disorders.

### **7.3.2 ADHD Rating Scale Version IV - Home Version (modified for investigator administration) (ADHD-RS-IV HV)**

The ADHD-RS-IV HV is used to assess the presence of clinically significant ADHD symptoms on Day -1.

The ADHD-RS-IV HV was developed to measure the behaviors of children with ADHD. The ADHD-RS-IV HV is a validated scale that consists of 18 items designed to reflect current symptomatology of ADHD based on Diagnostic and Statistical Manual for Mental Disorders Fourth Edition; Text Revision (DSM-IV-TR) criteria and is also consistent with DSM-5 criteria. Each item is scored from a range of zero (reflecting no symptoms) to 3 (reflecting severe symptoms) with total scores ranging from zero to 54. Higher ADHD-RS-IV HV total scores signify greater severity in ADHD symptoms.

The following ADHD-RS-IV HV scores will be assessed:

- ADHD-RS Total score (all items).
- ADHD-RS Hyperactivity/Impulsivity subscale score (even number items 2 through 18).
- ADHD-RS Inattentiveness subscale score (odd number items 1 through 17).

No imputation for missing ADHD-RS data will be performed. Descriptive statistics for the ADHD-RS-IV HV scores will be presented for each time point and data will also be presented in a listing.

## **7.4 Efficacy Outcomes**

### **7.4.1 Primary Efficacy Outcome**

The primary efficacy outcome is the change from baseline (Visit 4) at Day 15 (Visit 5) in ADHD symptoms as measured by mean SKAMP-CS obtained from an average of the 7 assessments collected across the 12 hour classroom day (12 to 24 hours post-dose).

### **7.4.2 Secondary Efficacy Outcomes**

Secondary efficacy outcomes include:

- Mean SKAMP-Combined score from the 7 assessments collected across the 12-

hour classroom day (12 to 24 hours post-dose) on Day 15

- SKAMP-Combined score at each of the assessment times (12-, 14-, 16-, 18-, 20-, 22-, and 24-hours post-dose) during the classroom day on Day 15
- Change from baseline at Day 15 in SKAMP-Combined score at each of the assessment times (12-, 14-, 16-, 18-, 20-, 22-, and 24-hours post-dose) during the classroom day
- Change from baseline at Day 15 in mean SKAMP-Attention subscale score obtained from the 7 assessments collected across the 12-hour classroom day (12 to 24 hours post-dose)
- SKAMP-Attention subscale score at each of the assessment times (12-, 14-, 16-, 18-, 20-, 22-, and 24-hours post-dose) during the classroom day on Day 15
- Change from baseline at Day 15 in SKAMP-Attention subscale score at each of the assessment times (12-, 14-, 16-, 18-, 20-, 22-, and 24-hours post-dose) during the classroom day
- Change from baseline at Day 15 in mean SKAMP-Depotment subscale score obtained from the 7 assessments collected across the 12-hour classroom day (12 to 24 hours post-dose)
- SKAMP-Depotment subscale score at each of the assessment times (12-, 14-, 16-, 18-, 20-, 22-, and 24-hours post-dose) during the classroom day on Day 15
- Change from baseline at Day 15 in SKAMP-Depotment subscale score at each of the assessment times (12-, 14-, 16-, 18-, 20-, 22-, and 24-hours post-dose) during the classroom day
- Change from baseline at Day 15 in Permanent Product Measure of Performance (PERMP)-Attempted and Correct Problems scores at each of the assessment times (12-, 14-, 16-, 18-, 20-, 22-, and 24-hours post-dose) during the classroom day
- PERMP-Attempted and Correct Problems scores at each of the assessment times (12-, 14-, 16-, 18-, 20-, 22-, and 24-hours post-dose) during the classroom day on Day 15
- Change from baseline at Day 15 in mean PERMP-Attempted scores obtained from the 7 assessments collected across the 12-hour classroom day (12 to 24 hours post-dose)

- Change from baseline at Day 15 in mean PERMP-Correct scores obtained from the 7 assessments collected across the 12-hour classroom day (12 to 24 hours post-dose)
- Change from baseline at Day 15 in mean PERMP total score (PERMP-Attempted + PERMP-Correct) obtained from the 7 assessments collected across the 12-hour classroom day (12 to 24 hours post-dose)

